8.2.8. Clinical Safety Laboratory Tests

- See Section 10.2 for the list of clinical laboratory tests to be performed and the SoA (Section 1.3) for the timing and frequency.
- The investigator must review the laboratory report, document this review, and record any clinically significant changes occurring during the study as an AE. The laboratory reports must be filed with the source documents.
- Abnormal laboratory findings associated with the underlying disease are not considered clinically significant unless judged by the investigator to be more severe than expected for the subject's condition.
- All laboratory tests with values considered clinically significantly abnormal during participation in the study or within 8 weeks after the last dose of study drug should be repeated until the values return to normal or baseline or are no longer considered clinically significant by the investigator or medical monitor.
 - a. If clinically significant values do not return to normal/baseline within a period of time judged reasonable by the investigator, the etiology should be identified, and the sponsor notified.
 - b. All protocol-required laboratory tests, as defined in Section 10.2, must be conducted in accordance with the laboratory manual and the SoA (Section 1.3).
 - c. If laboratory values from nonprotocol-specified laboratory tests performed at the institution's local laboratory require a change in subject management or are considered clinically significant by the investigator (eg, SAE or AE), then the results must be recorded within source documents.

8.2.9. Pregnancy Testing

- Refer to Section 5.1 Inclusion Criteria for pregnancy testing entry criteria.
- Pregnancy testing in WOCBP will be conducted throughout the study. A serum pregnancy test will be performed at screening and urine pregnancy testing will be performed at subsequent visits as detailed in the SoA (Section 1.3).
- Additional serum or urine pregnancy tests may be performed, as determined necessary by the investigator or required by local regulation or regulatory agency, to establish the absence of pregnancy at any time during the subject's participation in the study.

- The investigator is responsible for the review of medical history, menstrual history, and recent sexual activity to decrease the risk of inclusion of a woman with an early undetected pregnancy.

8.2.10. Hepatitis Testing

All subjects will be tested for the presence of HBV and HCV at screening. A positive result for the HBsAg will be exclusionary. Samples negative for HBsAg will be tested for HBsAb and HBcAb. If test results are positive for HBcAb or HBsAb, then HBV DNA PCR will be performed and any result that meets or exceeds detection sensitivity will be exclusionary. Positive HCV antibody tests at screening will be tested for HCV RNA by PCR; any detectable HCV RNA will be exclusionary.

8.2.11. Inflammatory Bowel Disease Screening

Given that subjects with psoriatic arthritis appear to have a higher lifetime risk of IBD compared to the general population and given that approved IL-17 inhibitors have reported worsening or new onset IBD in clinical trials, all subjects will be screened for IBD by history and a subset will undergo additional laboratory screening. During screening, all subjects will be assessed for the following symptoms within the last year:

- prolonged or recurrent diarrhea without established etiology
- prolonged or recurrent abdominal pain without established etiology
- blood in stool without established etiology
- any other symptoms in the opinion of the Investigator that may be suggestive of IBD

If any are marked affirmative, a fecal calprotectin test must be performed.

- If the resulting fecal calprotectin level is $> 150 - 500 \mu\text{g/g}$, the subject must undergo a GI consultation and obtain documented approval from the GI consultation to enroll in the clinical trial before continuing with the screening process. If the consultation cannot be completed within the screening window, the subject will be screen-failed but may rescreen.
- fecal calprotectin levels $> 500 \mu\text{g/g}$ will be exclusionary.

8.2.12. Tuberculosis Test

Determination of TB status will be required before the subject's inclusion in the study. A QuantiFERON test (or equivalent) will be performed on each subject to assess the TB status at screening. Subjects with a positive test result may not be included in the study (refer to [Section 5.1](#)). T-SPOT TB test may be used to establish eligibility if agreed upon with the medical monitor.

8.2.13. Rheumatoid Factor and Anti-cyclic Citrullinated Peptide Antibodies

All subjects will be tested for the presence of RF and anti-CCP antibodies at screening. Since these parameters are a potential indicator for rheumatoid arthritis, only subjects with a negative test result are eligible for participation in the study (refer to [Section 5](#)).

8.2.14. Home Study Drug Administration Diary

The subject (or caregiver/designee) will complete a diary for every study dose taken outside of the study site (ie, at home). The study drug should be administered on the dates as directed by the site staff. Information regarding the study drug administration (eg, date and time of study drug administration, if the full dose was administered) will be recorded in the study drug administration diary. Instructions on proper study drug administration will be provided to the subject (caregiver/designee). Subjects will be instructed to call the study site if they are having problems administering the study drug or have missed or delayed administering a dose. Subjects will be instructed to bring the study drug administration diary to each study visit.

8.3. Adverse Events, Serious Adverse Events, and Other Safety Reporting

The definitions of AEs and SAEs can be found in [Section 10.3](#).

Adverse events will be reported by the subject (or, when appropriate, by a care giver).

The investigator and any qualified designees are responsible for detecting, documenting, and recording events that meet the definition of an AE or SAE. The investigator is responsible for following up all AEs that are serious, considered related to the study drug or study procedures, or that caused the subject to discontinue the study drug (see [Section 7](#)).

The method of recording, evaluating, and assessing causality of AEs and SAEs and the procedures for completing and transmitting SAE reports are provided in [Section 10.3](#).

8.3.1. Time Period and Frequency for Collecting Adverse Event and Serious Adverse Event Information

All SAEs will be collected from the signing of the ICF until the 8-week follow-up visit at the timepoints specified in the SoA ([Section 1.3](#)).

All AEs will be collected from the first dose of study drug until the 4 weeks after the last dose of study drug as specified in the SoA ([Section 1.3](#)).

Medical occurrences that begin before the start of study drug but after obtaining informed consent will be recorded as medical history/current medical conditions, not as AEs.

All SAEs will be recorded and reported to the sponsor or designee immediately and under no circumstance should this exceed 24 hours from investigator's knowledge of the event, as indicated in [Section 10.3.4](#). The investigator will submit any updated SAE data to the sponsor within 24 hours of it being available.

Investigators are not obligated to actively seek information on AEs or SAEs after conclusion of the study participation. However, if the investigator learns of any SAE, including a death, at any

time after a subject has been discharged from the study, and he/she considers the event to be reasonably related to the study drug or study participation, the investigator must promptly notify the sponsor pharmacovigilance team.

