^a Visit/dosing windows of ±3 days on either side of the scheduled visits/dosing are permitted. In case of a delayed or missed dose, the investigator should return subjects on the original visit/dosing schedule in relation to Day 1 for subsequent doses. The window of ±3 days is relative to Day 1 and applicable for all subsequent visits/dosing. The minimum of time between doses should be no less than 4 days and no more than 10 days. Subjects do not need to return to the clinical site for dosing on weeks without study visits noted above if subject/caregiver completes study drug administration at home. See footnote “r” below.

^b Visit window of ±5 days. For subjects who prematurely discontinue study drug, the End of Treatment (EOT) visit should be completed within 14 days of withdrawal and follow-up visits should be completed at 8 weeks (Safety FU) and 14 weeks (PK & ADA FU) after the last dose of study drug, where possible. Subjects should continue to complete study assessments as outlined above where possible, with the exception of study drug administration. Anti-drug antibody sample and PK sample collection will not need to be completed if study drug is prematurely discontinued other than at the PK & ADA FU visit.

^c

All subjects who do not achieve cDAPSA low disease activity (cDAPSA ≤ 14) for 2 consecutive visits starting at Week 24 (e.g. at Week 20 and Week 24) will be required to discontinue study drug as described in Section 7.1. Participation in the study should be continued, with EOT visit and assessments as described in Section 4.1 and in footnote b and n.

^d Vital signs include measurements of temperature, respiratory rate, systolic and diastolic blood pressure, and pulse. Measurements should be taken in a sitting position after 5 minutes' rest.

^e Electrocardiograms in triplicate will be recorded (one minute apart) after subject has been supine for at least 5 minutes.

^f Chest x-ray (posterior/anterior or anterior/posterior) will be performed at screening in subjects who do not have a chest x-ray available within 3 months of screening. Women of childbearing potential must have a negative pregnancy test before an x-ray is performed.

^g Serious adverse events should be recorded from the signing of informed consent through the Safety Follow-up visit (ie, 8 weeks after the last dose of study drug); adverse events will be recorded from Day 1 (ie, administration of study drug) until 4 weeks after the last dose of study drug.

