9.3.5. Safety Analyses

Safety data will include summaries of exposure, AEs, TEAEs, SAEs, and laboratory data. No inferential statistics (*p*-values) will be reported for safety data.

Exposure will include the number of doses administered (including complete and incomplete doses) and reasons for missed or incomplete doses. Exposure will be reported through the planned collection of the primary endpoint and for the entire study. For subjects assigned to receive placebo who later receive izokibep, exposure will further be summarized by placebo and izokibep. Compliance will be summarized by placebo and izokibep and by phase (placebo controlled and after crossing over to active).

Adverse events and SAEs reported before the first administration of the study drug will be listed. All summaries will include only treatment-emergent events. The number of subjects who report 1 or more AEs, the number who report 1 or more severe AEs, the number who report 1 or more SAEs, and the number who report 1 or more AEs that lead to discontinuation of study drug will be summarized by treatment group during the primary phase of the study and overall. Subjects assigned to receive placebo who later receive izokibep will additionally be summarized by phase (placebo-controlled and after crossing over to active).

Laboratory data including ADAs will be summarized by treatment group and overall, at each planned collection timepoint.

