#### 5.1.3. Treatment Period

Data collected on Day 1 will be assigned to the Treatment Period unless the time (HH:MM) of data collection and time (HH:MM) of the first dose of study drug are both recorded and the data collection time is before the time of the first dose of study drug. In this case, the assessment will be assigned to the screening period. If the time (HH:MM) of data collection is not recorded but the protocol and/or eCRF includes an instruction to the effect that all Day 1 assessments are to be performed prior to the first dose of study drug, the data collected at Day 1 will be assigned to the screening period. However, adverse events and concomitant medications starting on Day 1, will be assigned to the Treatment Period, unless the time (HH:MM) demonstrates otherwise.

The Treatment Period is defined as the period from the date/time of the first dose of study drug to Week 52 (one week after the last dose) or early termination (end of treatment visit

should be completed within 14 days of withdrawal and follow-up visits should be completed at 8 weeks and 14 weeks after the last dose of study drug, where possible).

Treatment will be divided into two periods, Period 1 and Period 2, Period 1 will start at the first dose of study drug and ends at Week 16 when Week 16 assessments are completed and before administration of study drug. Period 2 will start at the time of administration of study drug at Week 16 and end at Week 52 or early termination/end of treatment visit.

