### 6.7.2. Adverse Events

All SAEs will be collected from the signing of the ICF until the 8-week follow-up visit. All AEs will be collected from the first dose of study drug until 4 weeks after the last dose of study drug. All AEs recorded on the eCRF will be coded using the latest MedDRA dictionary around the time of Database Lock and classified as either AEs or treatment-emergent AEs (TEAEs) as follows:

- TEAEs are either events with start date and time after the start of the Treatment Period and up to 4 weeks after the end of the Treatment Period, or events with start date and time prior to the start of the Treatment Period whose severity worsens on or after the start of the Treatment Period. TEAEs for period 2 are either events with start date and time after the start of administration of Week 16 treatment and up to 4 weeks after the end of the Treatment Period, or events with start date and time prior to the start of administration of Week 16 treatment whose severity worsens on or after the start of administration of Week 16 treatment. For subjects who receive treatment in period 2, TEAEs with start date after the start of period 2 will be assigned to period 2 only, not to period 1.
- Treatment-Emergent Serious AEs (TESAEs) will be defined as TEAEs which meet the criteria as Serious = “Yes”.
- The relationship between a TEAE and treatment is assessed as related or not related. A treatment-related TEAE will be defined as a TEAE considered by the investigator as related to treatment or with unknown/missing relationship to treatment.
- Assessment of AE severity will be based on eCRF AEs form.
- TEAEs leading to discontinuation of treatment are defined as TEAEs where “Action Taken with Study Treatment” is indicated as “Drug Withdrawn”.

In addition to the aforementioned AE types, the following TEAEs of special interest will be monitored:

- Candida infection,
- Inflammatory bowel disease,
- Suicidal ideation.
- Malignancies
- MACE (major adverse cardiovascular and cerebrovascular events: cerebrovascular accident and transient ischemic attack, non-fatal myocardial infarction or unstable angina, cardiovascular death)
- Tuberculosis (TB)
- Infections (serious, opportunistic, or fungal only)
- Cytopenias

- Systemic hypersensitivity reaction

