  - Subjects  $\geq$  65 years of age at baseline
- The number and percentage of subjects who died will be summarized
- The number and percentage of subjects reporting each TEAE and the number of events will be summarized by PT for all TEAEs
- The number and percentage of subjects reporting each TEAE and the number of events will be summarized by PT for TEAEs of Special Interest
- The number and percentage of subjects reporting each TEAE and the count of number of events according to the 5 Period 2 groupings as described in section 6.7 will be summarized by SOC and PT for the following types of TEAEs.
  - All TEAEs
  - Serious TEAEs

In the above summaries, subjects with more than one TEAE within a particular SOC are counted only once for that SOC. Similarly, subjects with more than one TEAE within a particular PT are counted only once for that PT.

For summaries by maximum severity, subjects with multiple TEAEs within a particular SOC or PT will be counted under the category of their most severe TEAE within that SOC or PT. TEAEs with missing severity will be included in the counts as severe (Grade 3) unless the TEAE has an outcome of fatal; in that case, the TEAE with missing severity will be included in the counts as death (Grade 5).

Summaries by SOCs and PTs will be sorted by SOCs by their Internationally Agreed Order (MedDRA) and PTs within SOC by descending order of total incidence. Where PTs tie, PTs will be sorted alphabetically.

All AE data will be listed and AEs and TEAEs will be presented together. Treatment-emergence status will be flagged in the listing. The listing will present the relative start and stop day of the AE calculated relative to the first dose of treatment and will be presented for those subjects who received at least one dose of treatment. If the AE is “Ongoing” it will be indicated as such in the listing and the relative stop day will not be calculated. Only original dates will be presented in the listing even though the relative day may be based on an imputed date.

In addition, the following listings will be presented:

- Listing of Deaths
- Listing of TEAEs
- Listing of Serious TEAEs
- Listing of AEs Leading to Interruption of Study Treatment
- Listing of AEs Leading to Discontinuation of Study Treatment
- Listing of AEs of Special Interest

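### SAEs that start in the last 3 weeks of collection (Weeks 56 to 59 for completers) enter no SAE table, because the treatment-emergent window closes first

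*Protocol*

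**What the plan says.** Collection. Protocol 8.3.1 states: "All AEs will be collected from the first dose of study drug until the 4 weeks after the last dose of study drug". Footnote g of the Schedule of Activities agrees: "adverse events will be recorded from Day 1 (ie, administration of study drug) until 4 weeks after the last dose of study drug". SAEs run longer. SAP 6.7.2, in line with Protocol 8.3.1, says: "All SAEs will be collected from the signing of the ICF until the 8-week follow-up visit".

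Reporting. SAP 5.1.3 runs the Treatment Period from first dose "to Week 52 (one week after the last dose) or early termination". SAP 6.7.2 counts an event as treatment-emergent if it starts "up to 4 weeks after the end of the Treatment Period". Serious events are a subset of these: "Treatment-Emergent Serious AEs (TESAEs) will be defined as TEAEs which meet the criteria as Serious". Protocol 9.3.5 adds: "All summaries will include only treatment-emergent events". Each serious-event table named in SAP 6.7.2 is a table of serious TEAEs.

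Listings and deaths. SAP 6.7.2 also says: "All AE data will be listed and AEs and TEAEs will be presented together", with treatment emergence flagged. It specifies listings of deaths and of AEs of special interest that are not limited to treatment-emergent events, and a count of subjects who died.

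Commitments. The protocol synopsis promises the incidence of each SAE. Protocol 9.4 and SAP 6.7.7 promise a summary of all safety data through the end of the study.

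**The concern.** The SAE collection window is tied to the last dose and lasts 8 weeks. The reporting window is tied to the end of the Treatment Period and lasts 4 weeks. The second closes before the first, so SAEs that sites must report for the full 8 weeks can fall outside every SAE count.

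At stake is the completeness of late safety tables. Arms are small (100, 100, 100 and 25), and several events named for monitoring are rare, such as serious infection, malignancy and major cardiovascular events. One late event can change a row. Leaving it out because two windows have different anchors would be hard to defend, and would not meet the promise to summarize all safety data to the end of the study.

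**Working it through.** **Inputs**
- Last dose at Week 51 and Safety Follow-up at Week 59 (Protocol 4.1).
- AE collection to 4 weeks, and SAE collection to 8 weeks, after the last dose (Protocol 8.3.1).
- End of Treatment Period at Week 52 for completers (SAP 5.1.3); treatment-emergent window 4 weeks beyond that (SAP 6.7.2).
- After early stopping, an end-of-treatment visit within 14 days of withdrawal (Protocol 4.1).
- 325 subjects planned.

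**The plan's own dates.** 51 + 8 = Week 59 and 51 + 14 = Week 65, both as stated. Maximum participation is 4 + 51 + 14 = 69 weeks, as stated in Protocol 4.1.4.

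**Completers**
- Non-serious AE collection ends at 51 + 4 = Week 55.
- The treatment-emergent window ends at 52 + 4 = Week 56.
- SAE collection ends at 51 + 8 = Week 59.
- Gap for SAEs: 59 - 56 = 3 weeks, or 21 days. With the 5-day visit window either way it is 16 to 26 days. As a share of post-dose SAE collection, 3/8 = 37.5%.
- There is also a 1-week mismatch the other way. In Week 55 to 56 a non-serious event would count as treatment-emergent but is no longer collected.

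**Early stoppers.** Assume that the end-of-treatment visit closes the Treatment Period and falls 0 to 14 days after the last dose. The treatment-emergent window then ends 28 to 42 days after the last dose. SAE collection ends at 56 days. Gap: 56 - 42 = 14 days to 56 - 28 = 28 days, that is 2 to 4 weeks.

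**Expected number of SAEs left out.** The documents give no long-term SAE rate, so 2 to 8 per 100 person-years is an assumption.
- All 325 subjects with a 3-week gap: 325 x 3/52 = 18.75 person-years. 0.02 x 18.75 = 0.38 and 0.08 x 18.75 = 1.5.
- With a 2-week gap: 325 x 2/52 = 12.5 person-years; 0.02 x 12.5 = 0.25.
- With a 4-week gap: 325 x 4/52 = 25.0 person-years; 0.08 x 25.0 = 2.0.

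**Residual drug.** With half-lives of 278 to 288 hours (Protocol 2.2.3.4) and a single-exponential decline, about 12% to 13% of drug remains 5 weeks after the last dose, when the gap opens for completers. By 8 weeks 3.5% to 4% remains.

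**The case against.** The strongest reply is that nothing is undetected. SAEs reach the sponsor within 24 hours throughout the 8 weeks. Late ones remain in the all-AE listing, and serious infections, malignancies, cardiovascular events and tuberculosis would also be in the special-interest listing. Deaths are listed and counted. All of this stands. A reader might infer that late SAEs vanish from the report, or survive only in the all-AE listing; the listings in SAP 6.7.2 do not support that. The gap is in tabulation: no SAE incidence table, and no entry in the listing of serious TEAEs.

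The size also rests on assumed rates. The earlier PsA study reported no serious AEs up to Week 16 (Protocol 2.2.3.3), so the true yield may be below the range shown. That stands, and it is why the point is modest.

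A further objection is that an 8-week window for serious events puts unequal follow-up into rows that count any TEAE. That is fair, and favors a separate SAE table or a clear footnote.

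A reader might also infer that stopping non-serious collection at 4 weeks is itself an error, because there is a Week 59 visit with laboratory tests and because other sections tell sites to record AEs without an end date. The documents do not support this:
- The 4-week stop is stated consistently in Protocol 8.3.1, Schedule footnote g and SAP 6.7.2.
- Section 5.6 is a general statement on COVID-19 precautions. Section 8.2.2 creates no Week 59 conflict, because the Schedule, as far as its table can be read, shows no examination at that visit.
- Section 8.2.8 already requires significant laboratory values within 8 weeks of the last dose to be repeated, and SAP 6.7.3 tabulates and grades the Week 59 results.

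The 4-week rule is a deliberate trade-off. A protocol amendment across about 100 sites is not justified by the small expected yield.

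**Conclusion.** The point holds as a reporting gap in the SAP. SAEs starting in the last 3 weeks of collection for completers, or the last 2 to 4 weeks for early stoppers, are collected but enter no SAE incidence table, and the commitment to summarize all safety data to the end of the study is not met for them.

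The expected size is about 0.4 to 1.5 SAEs, or 0.25 to 2.0 over the range of gaps. This rests on the assumed rate, on all 325 subjects contributing the full gap, and, for early stoppers, on the end-of-treatment visit closing the Treatment Period. SAP 5.1.3 does not say this plainly for subjects who stop drug but stay in the study.

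Efficacy is unaffected. So is the Week 0 to 16 safety comparison for subjects still on study drug at Week 16. Since the gap opens at least 4 weeks after the last dose, only someone who stops before about Week 12 (16 - 4) could have such an event inside that period. This is a cheap improvement in completeness and does not threaten the trial's conclusions.

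**What to change.** Change SAP 6.7.2 only:
- For serious events, set the reporting window as first dose to 8 weeks after the last dose. Alternatively, add one table of all SAEs starting after first dose through the Safety Follow-up visit; this avoids mixing follow-up lengths in the any-TEAE rows.
- Keep the 4-week window for non-serious events, but anchor it to the last dose so that it matches collection (Week 55 for completers).
- Footnote the two windows in the affected tables.
- Flag late SAEs that start after a new PsA therapy, using the concomitant-medication dates recorded to Week 65. The ban on other PsA drugs ends at Week 52 or on permanent discontinuation of study drug, so some late events may occur on other treatment.

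The cost is SAP wording and programming on data already collected, with no added burden on sites. No amendment to extend non-serious AE collection is needed. At most, Protocol 8.2.8 could be given an AE-recording end date consistent with 8.3.1.
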